1. RISKS TO THE SUBJECTS

a. Human Subjects Involvement and Characteristics

- Double-blind Prospective Randomized Control Trial
- Female or male patients 18 years or older
- Patients undergoing panniculectomy and agreeable to participate in the trial will be randomized to normal saline vs TXA
- Daily drain output will be monitored and recorded for each patient
- Rate of post-operative hematoma/seroma will be assessed by clinical evaluation to include palpation for ballotable fluid collection and assessment of skin for a shiny/tight appearance suggestive of an underlying fluid collection.
- Prisoners, pregnant or nursing women, persons under the age of 18, persons with preexisting coagulopathy, ongoing venous or arterial thrombosis, history of cerebral vascular accident, uncontrolled seizure disorder, documented administration of daily antiplatelet or anticoagulation (e.g. ASA, NSAIDs, Warfarin) or documented allergic reaction to tranexamic acid will be excluded from the study
- Patients can withdraw from the study at anytime

b. Sources of Materials

- All patient charts will be kept confidential, in compliance with HIPPA regulations
- All patient information will be stored on a password protected computer
- Normal saline and tranexamic acid are both products currently in use at the hospital in other plastic surgery procedures. They are indistinguishable in appearance, texture and odor; therefore, making them ideal substances for a double-blinded investigation
- No specimens will be stored

c. Potential Risks

- Potential risks include those risks associated with any surgical procedure.
- Patients will be monitored under standard operative protocols
- Although, the risks of topical use of TXA are not well known, there are known risks from oral and intravenous use. Those risks include:
 - o Allergic reaction
 - o Convulsions have been reported in association with intravenous tranexamic acid treatment in patients undergoing cardiovascular procedures
 - o Retinal changes have been documented in some animals receiving intravenous TXA for extended periods of time (days to weeks)
 - o Intravenous administration of tranexamic acid may cause dizziness
 - o Gastrointestinal disturbances may occur with intravenous administration

2. ADEQUACY OF PROTECTION AGAINST RISKS

a. Recruitment and Informed Consent

- Female or male patients > 18 years for abdominal panniculectomy will be offered participation

Reading Hospital – Tower Health Research Protocol

- Consent will be obtained by the provider performing the procedure
- Signed and witnessed consent will be placed within the patient's chart

b. Protection against Risk

- All patient charts will be kept confidential, in compliance with HIPPA regulations
- All patient information will be stored on a password protected computer
- All standard pre and post-operative photos will be stored on a password protected computer

3. POTENTIAL BENEFITS OF THE PROPOSED RESEARCH TO THE SUBJECTS AND OTHERS

- Our study aims to demonstrate a difference in hematoma rates as well as drain output between patients undergoing panniculectomy using topical tranexamic acid vs. normal saline. As a pilot study, these results could be used to encourage a larger investigation of the use of TXA in panniculectomy patients.

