**Reading Hospital – Tower Health
Research Protocol**

PI Name: [name].

**Study Title: Role of tranexamic acid (TXA) in the reduction of post-operative hematoma
and seroma in patients undergoing panniculectomy or abdominoplasty, a pilot study**

**NCT04902950
February 27, 2020**

Reading Hospital – Tower Health Research Protocol

PI Name: [name].

Study Title: Role of tranexamic acid (TXA) in the reduction of post-operative hematoma and seroma in patients undergoing panniculectomy or abdominoplasty, a pilot study

Other Investigators / Collaborators [name], D.O., [name], D.O., [name]., [name], D.O., [name].

Funding Source(s): Investigators will apply for funding from the Reading Hospital Foundation. If funding from the foundation is unavailable, investigators will seek other funding sources. If no funding is acquired, the investigators will cover the cost of the study drug.

A. SPECIFIC AIMS

We aim to investigate the use of tranexamic acid (TXA) as a hemostatic agent in abdominoplasty/panniculectomy. We believe tranexamic acid to be effective in decreasing hematoma rates and drain output, allowing for earlier drain removal.

B. RESEARCH QUESTION AND HYPOTHESIS

Does the use of TXA soaked sponges decrease hematoma rates and drain output, resulting in earlier drain removal in patients undergoing panniculectomy or abdominoplasty? Comparative outcomes including return to operating room, fluid collection requiring additional procedures (i.e. aspiration or percutaneous drainage), hematoma rates, daily drain output and time to drain removal will be measured between the control group (normal saline) and the experimental group (TXA). We are evaluating the potential for TXA to reduce drain output and decrease time to drain removal.

C. BACKGROUND AND SIGNIFICANCE

The antifibrinolytic drug, tranexamic acid (TXA) has proven to reduce blood loss and transfusion requirements in other fields of surgery including orthopedic, cardiac, craniofacial and gynecologic surgery. Metanalysis performed by Ker et al. concluded that TXA reduced blood loss by 29 percent and the need for blood transfusion by 49 percent over a variety of surgical procedures.¹ Masoomi et al. reviewed 20,130 patients who underwent abdominoplasty from 2007-2011, noting that 9.3 percent required a post-operative blood transfusion.²

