Each group will have 10 participants. Group 1 will undergo application of three normal saline soaked lap sponges to the surgical site, while Group 2 will undergo application of three TXA soaked lap sponges to the surgical site. After the abdominal skin and subcutaneous tissue is raised, the area will be irrigated, and hemostasis achieved using electrocautery. These steps are currently preformed with every panniculectomy. After hemostasis and irrigation, the soaked lap sponges will be unfolded and placed beneath the two lateral portions as well as the central area of the flap for 3 minutes. The lap sponges will not be “rung out” prior to placement. The time for TXA application is based on previous studies. The lap sponges will be removed after

Reading Hospital – Tower Health Research Protocol

three minutes. The surface area under the flap will be measured from the xiphoid process to the pubis, from the Xiphoid process to each anterior superior iliac spine (ASIS) and across from one ASIS to the other. These measurements will be used to calculate the surface area under the flap. These measurements will only be used in data collection and do not affect the principle aim of the study. The remainder of the surgical procedure will be the same for each patient. As currently practiced, two 15 round Blake drains will be placed for each patient. Patients will stay overnight for routine post-operative monitoring including vital signs and drain output or may be discharged home the same day of surgery if medically fit. Patients will also be monitored clinically at each post-operative visit for signs of post-operative hematoma or seroma.

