Data analysis for this project will consist of several parts. First it is important to analyze differences between the randomized control and treatment arms to test for bias. In order to do this, goodness of fit tests (GOF) will be performed on demographic variables such as age and gender. While the sample sizes are expected to be low, 10 for each arm, nonparametric tests consisting of Fisher's exact for discrete variables and Mann-Whitney U tests for continuous level data will be used. An omnibus p-value of 0.20 will be used to ensure there is no bias present in the samples. Secondly, efficacy analysis will be conducted on the outcome variables (drain output per day, total drain output, etc.) by use of Mann-Whitney U test. Statistically significant findings would be for a p-value less than 0.05 on any test. The samples are not expected to be large enough for the use of parametric measures so non-parametric methods will be used.

With a small sample of 10 patients per arm this analysis is viewed to be exploratory, and there will be no statistical corrections applied for multiple comparisons. Results of the GOF and efficacy analysis will be prepared and placed into tables for each group. In addition to the analysis mentioned above, power analysis will also be used to calculate the observed power for those tests with significant differences as well as to determine a sample size for those efficacy endpoints that did not achieve statistical difference. These power estimates will accompany the results in a separate table. Power analysis will be based on single tail alternative hypothesis with a power (1-B) of 80 percent and a p-value of 0.05. As this is an exploratory study, there will

Reading Hospital – Tower Health Research Protocol

be no interim analysis for efficacy or futility. The trial will be stopped after inclusion of twenty patients.

E. PROTECTION OF HUMAN SUBJECTS

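### With 10 patients per arm the pilot has almost no chance of showing a hematoma difference, and a sample size derived from its hematoma counts would usually be unobtainable or far too low

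*Combined protocol and SAP*

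**What the plan says.** Hematoma runs through the stated purpose. Section A opens with the belief "We believe tranexamic acid to be effective in decreasing hematoma rates and drain output". Section B lists, among the comparative outcomes, "hematoma rates, daily drain output and time to drain removal will be measured between the control group (normal saline) and the experimental group (TXA", alongside return to the operating room and collections that need a further procedure. Section E.3 goes furthest: "Our study aims to demonstrate a difference in hematoma rates as well as drain output".

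On size, section D says "Each group will have 10 participants" and "The trial will be stopped after inclusion of twenty patients". It calls the analysis exploratory.

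On analysis, section D names the Mann-Whitney U test for the efficacy outcomes, giving two drain-output measures as examples and leaving the list open. Fisher's exact test is named for discrete variables in the baseline comparison. The criterion is "Statistically significant findings would be for a p-value less than 0.05 on any test", with no sidedness given. Section D then plans observed power for the significant tests, and for the others to "determine a sample size for those efficacy endpoints that did not achieve statistical difference", using a one-tailed alternative, 80% power and 0.05. Yes/no outcomes are not excluded, and nothing covers zero or equal counts.

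**The concern.** Hematoma is a yes/no event that may be uncommon. Ten patients per arm give a handful of events at most, so a comparison at 0.05 is likely to be non-significant whatever TXA does. Section D would then send hematoma to the sample-size step, where the input is a difference between two counts out of ten. If the counts are equal or favor saline, there is no benefit to size for. If they favor TXA, one event more or less changes the answer several-fold.

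Two things are at stake. One is the interpretation of a non-significant hematoma result. The other is the pilot's main product: E.3 offers the results as grounds for a larger study, and that study could be sized from a number with little relation to the truth.

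**Working it through.** **Inputs.** From the documents: 10 per arm; criterion 0.05; Mann-Whitney for efficacy, Fisher for discrete baseline variables; sample-size step one-tailed, 80% power, 0.05. Not given: any hematoma rate, any target difference, and the sidedness of the efficacy tests. I assume control rates of 5%, 10% and 20%, either halved or abolished by TXA, and show both sidednesses. The figure of 10 per arm is stated without inputs, so there is nothing to reproduce it from.

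**1. Smallest significant split with no TXA events.**
- Fisher, k vs 0: one-sided p = C(10,k)/C(20,k), doubled for two-sided. For k = 4: 210/4845 = 0.043 one-sided, 0.087 two-sided. For k = 5: 252/15504 = 0.016 and 0.033. So 5 control hematomas are needed two-sided, 4 one-sided.
- Asymptotic Mann-Whitney on 0/1 data, tie-corrected: z = √(19/20) × (difference)/√(p̄(1−p̄)×2/10). For 3 vs 0: 0.975 × 0.3/0.160 = 1.83, p = 0.067 two-sided, 0.034 one-sided. For 4 vs 0: 0.975 × 0.4/0.179 = 2.18, p = 0.029 two-sided. So 4 are needed two-sided, 3 one-sided. A continuity correction does not move these thresholds.

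**2. Power**, summing binomial probabilities over all 11 × 11 pairs of counts with p < 0.05:

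| Control vs TXA | Fisher 2-sided | Fisher 1-sided | Mann-Whitney 2-sided | Mann-Whitney 1-sided |
|---|---|---|---|---|
| 5% vs 2.5% | 0.01% | 0.08% | 0.08% | 0.9% |
| 10% vs 5% | 0.1% | 0.8% | 0.8% | 4.3% |
| 20% vs 10% | 1.2% | 4.5% | 4.6% | 12.6% |
| 10% vs 0% | 0.2% | 1.3% | 1.3% | 7.0% |
| 20% vs 0% | 3.3% | 12.1% | 12.1% | 32.2% |

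The last two rows are simple binomial tails: at 20% vs 0%, P(at least 5, 4 or 3 of 10) = 3.3%, 12.1%, 32.2%.

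**3. Sample-size formula**, per arm, with the plan's one-tailed 0.05 and 80% power:

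n = [1.645√(2p̄(1−p̄)) + 0.842√(p₁(1−p₁) + p₂(1−p₂))]² / (p₁−p₂)²

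- True need at 10% vs 5%: (0.613 + 0.312)²/0.0025 = 342.1, so 343.
- Observed 1 vs 0: (0.507 + 0.252)²/0.01 = 57.7, so 58.
- Observed 2 vs 0: (0.698 + 0.337)²/0.04 = 26.8, so 27.
- Observed 2 vs 1: 157. Observed 3 vs 2: 231.

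**4. What the step would return if TXA truly halves the rate**, feeding it the observed rates:

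| Control vs TXA | True n per arm | Equal counts (0 vs 0 alone) | More TXA events | No benefit to size | n under half the truth | n within factor 2 |
|---|---|---|---|---|---|---|
| 5% vs 2.5% | 714 | 52.9% (46.5%) | 14.2% | 67% | 32.9% | 0% |
| 10% vs 5% | 343 | 34.6% (20.9%) | 17.6% | 52% | 47.3% | 0.4% |
| 20% vs 10% | 157 | 21.3% (3.7%) | 16.5% | 38% | 45.0% | 16.1% |

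The small remainder is trials significant by two-sided Fisher. As a check on one entry, 0 vs 0 at 10% vs 5% is 0.9¹⁰ × 0.95¹⁰ = 0.349 × 0.599 = 0.209.

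**5. What 10 patients do say.** For 0 of 10, the exact 95% upper limit is 1 − 0.025^(1/10) = 0.308, so the interval is 0–31%.

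**The case against.** The strongest reply has four parts.

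*Section D does not say this.* It does not list hematoma among the tested outcomes or state that observed rates feed the sample-size step. That stands: both are inferences. They are the natural reading, because the outcome list is open, section B names hematoma rates as a comparative outcome, the same sentence speaks of observed power, and no other source of effect size is named.

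*The result is not fixed in advance.* A reader might infer that the trial cannot show a difference. The documents do not support that. A 5 vs 0 split is significant by any of these tests, and if the efficacy test is one-sided Mann-Whitney, 3 vs 0 suffices.

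*The rates are assumed.* They are. The clinical criterion in E.1.a, "palpation for ballotable fluid collection", could also pick up more collections than hematoma alone. At 30% vs 15%, two-sided power is still 3.4% (Fisher) or 9.0% (Mann-Whitney), and TXA events equal or exceed control events in 15.6% + 13.5% = 29% of trials. The sizing step does better if the effect is extreme: at 20% vs 0%, the derived n is within a factor of two of the truth in 50% of trials. So the size of the problem depends on the rates, but low power persists.

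*It is an exploratory pilot.* The title and section D say so, and this tempers the aim. It does not withdraw the verb in E.3 or the sample-size step. A reader might also infer that the plan would call a non-significant result no effect; nothing in it says that. It simply does not guard against it.

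**Conclusion.** The point holds in this form: over most of the assumed range, 10 per arm gives almost no chance of showing a hematoma difference, and sizing a later trial from the observed hematoma counts would usually fail. At 10% vs 5%, power is 0.1% to about 4% depending on test and sidedness; no sample size for a benefit can be derived in 52% of trials, and the derived n is within a factor of two of the true 343 per arm in about 0.4%. The most favorable power case tried within the 5–20% range, abolition of a 20% rate with one-sided Mann-Whitney, reaches 32%.

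This rests on assumed control rates of 5–20%, on exactly 10 evaluable patients per arm, and on the reading that hematoma and its observed rates enter the sample-size step. It concerns yes/no outcomes only. A reader might infer that the trial must enroll more patients, or that hematoma and seroma must be merged into a composite. Neither follows: the mismatch is between this endpoint and the stated aim and rule, and it can be removed at the present size. The drain-output analyses are not touched.

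**What to change.** For hematoma, seroma, collections needing a procedure and return to the operating room:

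1. In E.3, and consistently in A and B, state the aim as estimating hematoma rates, not demonstrating a difference in them.
2. In section D, report counts per arm with exact 95% intervals for each rate and for the difference between arms. State that a non-significant result is not to be interpreted as no effect.
3. Exclude these outcomes from the sample-size table based on observed data. Instead tabulate n per arm over stated assumed control rates (for example 5–20%) and a stated relative reduction. With halving, the one-tailed 80% power entries are 714, 343 and 157 per arm at 5%, 10% and 20%.

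The cost is a few sentences and one table; enrollment, procedures, data collection and the drain-output analyses are unchanged. The downside is small: the pilot gives up a hematoma efficacy claim that it could hardly have supported.

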4. IMPORTANCE OF THE KNOWLEDGE TO BE GAINED

- This study allows us to investigate additional methods to achieve low drain outputs in panniculectomy. The knowledge gained from our proposed study will be applicable to patients undergoing panniculectomy. In addition, this method of achieving hemostasis may lead to further research studies for various other surgical procedures.

5. SUBJECT SAFETY AND MINIMIZING RISKS (Data and Safety Monitoring Plan)

Subject safety will be monitored by the physician performing the procedure.

- Subjects will be monitored for allergic reaction, wound healing complications, venous thromboembolism, drain output, and time to drain removal.
- Subjects will be monitored during their overnight hospital stay, if overnight admission is deemed appropriate. Participants will also be evaluated at each follow-up visit. Patients will be scheduled for follow-up at one week, three weeks, and eight weeks following their procedure.
- The physician performing the procedure will be responsible for the monitoring and evaluating patients postoperatively.
- This investigational study aims to assess for any difference in drain output, time to drain removal or return to the OR for hematoma or seroma evacuation.

F. REFERENCES/LITERATURE CITATIONS

3. Reed and Woolley. Uses of tranexamic acid. Continuing education in anaesthesia, Critical Care & Pain. 2015; 15(1):32-37.

Reading Hospital – Tower Health Research Protocol

6. Rohrich RJ and Cho MJ. The role of tranexamic acid in plastic surgery: review and technical considerations. *Plast Reconstr Surg.* 2018 Feb; 141(2):507-515.

G. CONSULTANTS

Our statistician is a consultant for the hospital.

H. FACILITIES AVAILABLE

Our trial will be conducted through Tower Health Reading Hospital Medical Center and its associates.

I. INVESTIGATOR BROCHURE

N/A

J. APPENDIX

Attach any additional information pertinent to the project such as:

- surveys or questionnaires,
- diaries or logs,
- informed consent and/or HIPAA authorization documents, etc.
